The BRAIN App: Building Relationships Using Artificial Intelligence and Nostalgia NCT05515679

Study Protocol 7/27/22

STUDY OVERVIEW

Study Title:

The BRAIN App: Building Relationships using Artificial Intelligence and Nostalgia

This is a quasi-experiment using a pre-post design—i.e., baseline vs. treatment / post-treatment. The study investigates the effects of an Artificial Intelligence-enabled Cognitive Stimulation Therapy (CST) app on persons with dementia (PWD). The primary objective is to examine the impact of the app on engagement / affect. More specifically, the study will examine whether the app produces increases in Constructive Engagement, Passive Engagement, and Pleasure and/or decreases in Other Engagement, Non-Engagement, and Anxiety/Sadness. A secondary objective is to examine the impact of the app on quality of life, neuropsychiatric symptoms, and the quality of the carer-patient relationship.

This study will be conducted at one CCRC, in their nursing home (NH) and assisted living facility (ALF). The study will involve 24 PWD (12 from a NH and 12 from an ALF), 20 staff members (10 from a NH and 10 from an ALF), and 24 family members (12 related to PWD from a NH and 12 related to PWD from an ALF). PWD will be 65+ years old, diagnosed with any type of dementia, and speak and read English. In addition, the exhibit at least one responsive behavior at baseline, based upon the NPI-NH (Neuropsychiatric Inventory-Nursing Home) and/or score below the maximum on the Dementia Quality of Life (DEMQOL) scale. To accommodate for attrition, 28 PWD, 24 Staff Members, and 28 Family Members will initially enroll in the study.

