2. DEMQOL

- a. A researcher will conduct a direct interview with the PWD to conduct the DEMQOL. However, if the PWD is unable to respond to questions on the DEMQOL, this measure will be collected via proxy interview (with a staff member who is familiar with the PWD.
- b. The DEMQOL is a 28-item self-reported measure related to health-related quality-of-life (HRQL) in patients with dementia. The DEMQOL takes cognition, negative emotion, positive emotion, social relationships, and loneliness into consideration. The DEMQOL-Proxy is a 31-item test completed by the caretaker and focuses on cognition, negative emotion, positive emotion, daily activities, and appearance.
 - i. Each item on the DEMQOL (and DEMQOL-Proxy) has four options:

Not at all

A Little

Ouite a Bit

A Lot

ii. Most items are scored as follows

Not at all = 4

A Little = 3

Quite a Bit =2

A Lot=1

iii. However, since some questions are worded differently, they are reverse coded in the following manner:

Not at all = 4

A Little = 3

Quite a Bit =2

A Lot=1

- iv. The total possible score on the DEMQOL ranges from 28 112, with lower scores indicating a lower quality of life.
- v. There is also a 29th item on the DEMQOL, which asks the PWD to rate his/her overall quality of life. this item has the following options and coding:

Poor = 1

Fair = 2

Good = 3

Very Good = 4

vi. This final item is not included in the total score on the DEMQOL

3. Document All Diagnoses, Type of Dementia, Meds, and Demographics

a. A researcher will conduct a CHART REVIEW to collect the following data:

- i. All diagnoses
- ii. Type of dementia
- iii. All meds
- iv. Demographics (race/ethnicity, education level, marital status, and number of years living in LTC)

4. Observations of PWD in Standard Activities w/ MPES

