2. DEMOOL

a. A researcher will conduct a direct interview with the PWD to conduct the DEMQOL. However, if the PWD is unable to respond to questions on the DEMQOL, this measure will be collected via proxy interview (with a staff member who is familiar with the PWD. The DEMQOL is described above.

PLEASE NOTE: all of the above measures will be completed 61-74 days after the informed consent document and assent form are signed.

Staff Members

Screening

After obtaining consent from the staff member, the following procedures will be followed to determine whether the staff member is eligible for the study. The Screening Process will occur 1-7 days after the informed consent document is signed.

- 1. A researcher will conduct a DIRECT INTERVIEW with the staff member determine whether the PWD meets the following criteria:
 - a. He/she is age 18+
 - b. He/she is able to read and speak English
 - c. He/she does not only work third shift

PLEASE NOTE: The above screening process will occur 1-8 days after the consent is signed.

Baseline Assessments

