After consent is obtained from the PWD's legally authorized representative and the PWD him/herself provides assent, a researcher will schedule a time with staff at the nursing or assisted living to review eligibility information in his/her chart (i.e., age 65+, able to read and speak English, diagnosed with dementia (of any type), NOT bed confined, NOT completely unable to communicate verbally, does NOT have serious visual or hearing impairments, and does NOT show signs of rapid cognitive decline or physical deterioration over the last 6 months).

NPI-NH Interview

A researcher will then schedule a time to interview a staff member familiar with the PWD to conduct the NPI-NH. The researcher will follow standard protocol for conducting the NPI-NH and be extensively trained on how to properly use the measures.

Baseline Procedures

Baseline Assessment

A researcher will schedule a time to work with the PWD and conduct a direct interview with him/her to complete the DEMQOL and BIMS. The researcher will follow standard protocol for conducting these measures and be extensively trained on how to properly use these measures. *Please note that the BIMS is not an outcome measure. The BIMS is exclusively being conducted so that we can describe the level of impairment of the study sample.*

Chart Review

A researcher will schedule a time with staff at the nursing or assisted living to collect the following data from his/her chart:

- All diagnoses
- Type of dementia
- All meds
- Demographics (race/ethnicity, education level, marital status, and number of years living in LTC)

Observations of Standard Activities

Researchers will observe the PWD taking part in standard activities using the MPES and EPWDS. At least 12 observations will be taken with each measure, so that an average score can be calculated for baseline, standard activity programming. Researchers will follow the standard protocols for using the MPES and EPWDS and be extensively trained on how to properly use these measures.

Intervention Period Procedures

The PWD will be invited to participate in three BRAIN sessions per week for four weeks. The sessions will be facilitated by a staff member at the nursing home or assisted living facility. The staff member will be trained on how to conduct BRAIN Sessions.

Treatment Fidelity / Process Measures

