- Follow-up visit at a time point different from that specified in the protocol

A screenshot of the Protocol Deviation / Violation Log is included in the Appendix.

DATA COLLECTION AND STUDY FORMS

The following documents are used in this study. Descriptions of measures are included above. The measures themselves are also included in the Appendix.

PWD

Screening Documents (1-7 days after consent/assent)

- 1. Chart Review Form for PWD Inclusion Criteria
- 2. NPI-NH

Baseline Assessments / Observations Documents (8-30 days after consent/assent)

- 1. BIMS
- 2. DEMQOL
- 3. Chart Review Form for Diagnoses, Type of Dementia, Meds, and Demographics
- 4. MPES
- 5. EPWDS

Intervention Period Data Collection (31-60 days after consent/assent)

- 1. Session Summary Form
- 2. MPES
- 3. EPWDS
- 4. PWD Satisfaction Question Form

Post-Treatment Assessment Documents (61-74 days after consent/assent)

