1. QCPR

Family Members

Screening Documents (1-7 days after consent/assent)

1. Interview Form for Family Member Inclusion Criteria

Baseline Assessments / Observations Documents (8-30 days after consent/assent)

1. Life Story Questionnaire

ALL FORMS ARE INCLUDED IN THE APPENDIX.

Source Documentation

This section describes how participant data are maintained in the study.

Definitions: A source document is any document on which study data are initially recorded. Source documents for this study include demographics forms, medical records, standardized test forms, satisfaction questionnaires, and engagement forms, etc. Most source documents are electronic in nature and will also serve as eCRFs to document study-specific data requirements. This method reduces the likelihood of transcription errors. All data will be checked and cleaned during a QA process to ensure data integrity.

All essential study documents will be retained by the investigator in an electronic Participant Binder and include:

- Source documents
- Signed informed consent forms

- Questionnaires completed by the participant
- Questionnaires completed by the proxy interviews
- Case Report Forms (CRFs)
- Data correction forms
- Applicable *Notes to File*

At conclusion of study, all source documents, CRPs, and other required documentation is kept with study records as required by protocol and IRB guidelines.

Forms Maintenance

All forms will be stored in electronic participant "binders" (file folders on the Hopeful Aging server). Forms which are collected digitally will automatically be saved to a secure, HIPAA-compliant database and then manually distributed to the correct participant binder. Hard copy forms will be scanned and placed into the proper binder.

General Instructions for Completing Forms

For All forms:

- All forms should filled out electronically, unless internet is unavailable.
- Completed forms should be saved in the participant's digital binder (file folder with their ID number)
 - o Naming Convention should be as follows:
 - o MM/DD/YYYY/ ID# Name of File
- All forms need to be reviewed by the Experimental Team Leader before being entered into SPSS.
- After being reviewed the Experimental Team Leader should initial the form, indicate the date, and make the file read only.
 - o Reviewed by [name] on 7/1/2022 at 4:30pm
- The Experimental Team Leader is responsible for updating forms, as needed.
- The PI will review and approve all changes to forms.

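### The DEMQOL key labelled as reversed repeats the standard key; if scored as printed, the reversed items count in the wrong direction in the quality-of-life change

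*Protocol*

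**What the plan says.** The scoring rule is in the Protocol, Baseline Assessments / Observations, 2. DEMQOL, part b. It is introduced for the 28-item DEMQOL and the 31-item DEMQOL-Proxy together.

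- Sub-item ii opens "Most items are scored as follows" and gives four values.
- Sub-item iii continues "However, since some questions are worded differently, they are reverse coded in the following manner" and gives four values again. They are the same four.
- Sub-item iv gives the DEMQOL total a range of 28 to 112, "with lower scores indicating a lower quality of life".

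The post-treatment assessment prints no key of its own: "The DEMQOL is described above". Under Visit Procedures, Baseline Assessment, "The researcher will follow standard protocol for conducting these measures", and training is promised. Data Collection and Study Forms places the instruments elsewhere: "The measures themselves are also included in the Appendix".

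The Study Overview lists quality of life as a secondary objective. The SAP tests DEMQOL by a paired t-test and gives no scoring rule.

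**The concern.** An item needs reversing when agreement with it signals good rather than poor quality of life. On the standard key, such an item gives its lowest score to the person who is doing best. The Protocol recognises this, says it will reverse those items, and then prints a key that does not.

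DEMQOL is the plan's only quality-of-life outcome, and this is the only scoring rule printed for it. Using the same wrong key at both visits does not cancel the error. The change on each reversed item takes the opposite sign, so the analysed quantity becomes the change on the standard items minus the change on the reversed items.

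The planned checks could miss it. The range check under Data and Form Checks sees only permissible totals, and the double check at data entry verifies the entered data rather than the key.

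**Working it through.** **The two keys side by side**

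| Response | Key for most items (ii) | Key labelled as reversed (iii) | True reversal (5 − score) |
|---|---|---|---|
| *Not at all* | 4 | 4 | 1 |
| *A Little* | 3 | 3 | 2 |
| *Quite a Bit* | 2 | 2 | 3 |
| *A Lot* | 1 | 1 | 4 |

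Columns ii and iii agree in all four rows.

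**The plan's own figure.** The range is 28 × 1 = 28 to 28 × 4 = 112, as stated. It is the same whichever key is used. For the Proxy the corresponding range is 31 × 1 = 31 to 31 × 4 = 124. A range check therefore cannot detect the error in either version.

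**Inputs.** Item counts of 28 and 31 come from the DEMQOL section. The number of reversed items, k, is not given. Since the standard key covers most items, k lies between 1 and 13 of 28, or between 1 and 15 of 31. The values k = 3, 5 and 8 below are illustrations.

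**Best true quality of life.** Scored as printed, this person gets 4(28 − k) + k = 112 − 3k.

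**Share of the change kept, if every item changes equally.** For J items it is (J − 2k)/J.

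**Sign change.** This needs k × (gain per reversed item) to exceed (28 − k) × (gain per other item), so the gain ratio must exceed (28 − k)/k.

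**Inflation example.** Suppose the other items gain 0.5 each and the reversed items lose 0.5 each. The true change is 0.5(28 − 2k); the scored change is 0.5 × 28 = 14.

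| | k = 3 | k = 5 | k = 8 |
|---|---|---|---|
| Score at best true quality of life (should be 112) | 103 | 97 | 88 |
| Change kept, 28 items | 22/28 = 79% | 18/28 = 64% | 12/28 = 43% |
| Change kept, 31 items | 25/31 = 81% | 21/31 = 68% | 15/31 = 48% |
| Gain ratio needed for a sign change | 8.3 | 4.6 | 2.5 |
| Inflation example: true change (scored +14) | +11 | +9 | +6 |

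At the extremes for 28 items, k = 1 keeps 26/28 = 93% and k = 13 keeps 2/28 = 7%.

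**Power of the paired t-test.** The documents give no effect size for DEMQOL. Assume n = 24 (the Study Overview target), a two-sided 5% test, and a standardised change of d = 0.597, which gives 80% power when scored correctly. Let all items have the same mean change and SD, with correlation r between true item changes. Then

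scored d = 0.597 × [(28 − 2k)/28] × √{[28(1 − r) + 784r] / [28(1 − r) + r(28 − 2k)²]}.

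| r | k = 3: d, power | k = 5: d, power | k = 8: d, power |
|---|---|---|---|
| 0 | 0.469, 60% | 0.384, 44% | 0.256, 22% |
| 0.1 | 0.557, 74% | 0.515, 68% | 0.414, 49% |
| 0.3 | 0.583, 78% | 0.567, 76% | 0.516, 68% |
| 0.6 | 0.593, 79% | 0.588, 79% | 0.569, 76% |

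A simulation of 8,000 runs gave 61%, 43% and 23% at r = 0, and 80%, 78% and 76% at r = 0.6. For k = 1, power is 74% (r = 0) to 80% (r = 0.6). For k = 13 it is 22% at r = 0.6 and lower for smaller r.

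**Eligibility.** The Screening and Eligibility Criteria sections use the NPI-NH alone, and the visit schedule puts DEMQOL (Days 8-30) after enrollment (Days 1-7), so that rule is unaffected. The Study Overview also mentions having to "score below the maximum on the Dementia Quality of Life (DEMQOL) scale". Under that wording, a person with the best true quality of life would score 112 − 3k and wrongly count as below 112.

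**The case against.** The strongest reply is that this is a copy-and-paste slip and not a planned scoring rule. The label and the direction of the total both show the intent, and a careful reader would see a typing error. The working forms are in an appendix not supplied here: "ALL FORMS ARE INCLUDED IN THE APPENDIX". Researchers are to be trained and to follow the standard procedure, and a statistical consultant assists with the analysis. Nothing shows that the printed key was used. It is also fair to say that the power figures rest on k, r, the starting power and equal item changes, none of which the documents give. The lowest powers need item changes within one scale to be independent. The sign-change and inflation cases need uneven or opposite item movement.

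Most of this stands as a limit on the likely harm. It does not remove the contradiction. The reference to standard procedure concerns conducting the measure and changes no printed value. No supplied text gives another key or identifies the items, and the post-treatment section points back to this one. The only written scoring rule for a tested outcome should not depend on readers noticing that it is wrong.

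**Conclusion.** The concern holds and should be fixed. That the two keys are identical, against the label and the stated direction, is certain from the text. Harm to the results is conditional: it arises only if the printed key is applied, which the documents neither show nor exclude.

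If it is applied, the firm consequence is a wrong reported quality-of-life change whenever the reversed items change. Under equal item change it shrinks to (28 − 2k)/28 of the truth, between 93% and 7% over the values of k that the text allows. Loss of power is a lesser matter if few items are reversed and item changes are correlated. The error is confined to this secondary outcome and, through the Study Overview wording only, to one eligibility alternative. The primary MPES and EPWDS analyses are not affected.

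**What to change.** - In the DEMQOL section, change the reversed key to *Not at all* = 1, *A Little* = 2, *Quite a Bit* = 3, *A Lot* = 4.
- List the reversed item numbers for the 28-item and 31-item versions in the Protocol or SAP.
- Confirm that the appendix forms and the SPSS scoring agree with that key and list.
- If any totals were made with the printed key, rescore both visits from the retained item responses before the paired t-test.

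The cost is four values, one item list covering both versions, and one check of form and scoring. No new data are needed, since participant forms are kept for 3 years after the study ends.

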1. NPI-NH

a. The NPI-NH will be conducted by a researcher by interviewing a staff member who is familiar with the PWD. The NPI-NH is described above.

2. DEMOOL

a. A researcher will conduct a direct interview with the PWD to conduct the DEMQOL. However, if the PWD is unable to respond to questions on the DEMQOL, this measure will be collected via proxy interview (with a staff member who is familiar with the PWD. The DEMQOL is described above.

PLEASE NOTE: all of the above measures will be completed 61-74 days after the informed consent document and assent form are signed.

Staff Members

Screening

After obtaining consent from the staff member, the following procedures will be followed to determine whether the staff member is eligible for the study. The Screening Process will occur 1-7 days after the informed consent document is signed.

- 1. A researcher will conduct a DIRECT INTERVIEW with the staff member determine whether the PWD meets the following criteria:
 - a. He/she is age 18+
 - b. He/she is able to read and speak English
 - c. He/she does not only work third shift

PLEASE NOTE: The above screening process will occur 1-8 days after the consent is signed.

Baseline Assessments

1. OCPR

- a. A researcher will conduct a direct interview with the staff member to conduct the OCPR.
- b. The QCPR is a 14-item scale measures warmth and/or absence of conflict or critique on a 5-point Likert scale, ranging from "totally disagree" to "totally agree."
 - i. For warmth/affection items, "totally disagree" responses are scored with one point and "totally agree" responses are scored with five points. Intermediate responses are scored with two, three, or four points.
 - ii. For conflict/criticism items, "totally agree" responses are scored with one point and "totally disagree" responses are scored with five points. Intermediate responses are scored with two, three, or four points.
 - iii. A score under 42 reflects a poor relationship, while a score over 56 reflects a good relationship. The remaining scores (between 42 and 56) indicate that the quality of the relationship is common, i.e., a standard relationship (Spruytte et al., 2002).

2. Pre-Training Quizzes for Training Modules

- a. Staff will be asked to complete two 15-item quizzes--i..., one 15-item quiz for "Training Module 1: Using the BRAIN App" and one 15-item quiz for "Training Module 2: Top 10 Tips for Facilitating Activities with Persons with Dementia."
- b. All questions will be multiple choice in nature.
- c. Staff will complete the quizzes independently on a computer, tablet, or smartphone

PLEASE NOTE: the above measures will be completed 8-30 days after the informed consent document is signed.

Intervention Period Data Collection

1. Take Two Training Modules

- a. During the first week of the Intervention Period, the staff member will take the two online training modules:
 - i. Training Module 1: Using the BRAIN App
 - ii. Training Module 2: Top 10 Tips for Facilitating Activities with Persons with Dementia

2. Learning Management System Automatically Collects Basic Training Data

- a. The Learning Management System will automatically collect two pieces of data for each training module:
 - i. Did the Staff Member complete the training module? (Yes/No)
 - ii. How long did it take for the Staff Member to complete the training module (in minutes)?

3. Post-Training Quizzes for Training Modules

a. After completing each training module, the Staff Member will be presented with the two 15-item quizzes that were presented to them at baseline (although the order of the questions will be changed).

4. Treatment Fidelity / Process Measures

a. The Staff Member will be invited to facilitate three BRAIN sessions per week for

four weeks (for each PWD). A Session Summary Form will be completed for each scheduled session, even if the session does not actually occur due to the PWD's unavailability or refusal to participate. The following data will be collected on the Session Summary form:

- i. PWD ID#
- ii. Date of Session
- iii. Time of Session
- iv. Facilitator ID#
- v. Did the PWD attend the session? (Yes/No)
 - 1. If NO to previous question, please indicate why the PWD did not attend? (Unavailable / Refused / Other)
 - 2. Reason for unavailability or refusal
- vi. Length of Session

5. Satisfaction Questions

- a. at the end of each session a researcher will pose the following three questions to the PWD:
 - i. Did you enjoy facilitating the activity? Yes/No
 - ii. Do you think the PWD enjoyed the activity? Yes/No
 - iii. Would you facilitate an activity like this again sometime? Yes/No
 - iv. Would you recommend this activity to your colleagues? Yes/No

PLEASE NOTE: all the above measures will be completed during the Intervention Period, which occurs 31-60 days after the informed consent document is signed.

Post-Treatment Assessments

1. OCPR

a. A researcher will conduct a direct interview with the staff member to conduct the QCPR. The QCPR is described above.

PLEASE NOTE: all the above measures will be completed during the Intervention Period, which occurs 31-60 days after the informed consent document is signed.

Family Members

Screening

After obtaining consent from the family member, the following procedures will be followed to determine whether the family member is eligible for the study. The Screening Process will occur 1-30 days after the informed consent document is signed.

- 1. A researcher will conduct a DIRECT INTERVIEW with the family member determine whether the PWD meets the following criteria:
 - a. He/she is age 18+
 - b. He/she is able to read and speak English

PLEASE NOTE: The above screening process will occur 1-30 days after the consent is signed.

Baseline Assessments

1. Life Story Questionnaire

- a. FMs will be asked to fill out the Life Story Questionnaire to provide information about their loved one's background and interests. The questionnaire will be filled out on a computer, tablet, or smartphone. Simple questions with radio buttons and checkboxes will be used, as well as open text fields.
- b. The following categories of information will be included: demographics, hometown, childhood, relationships, previous occupation, hobbies, social preferences, sports interests, TV/movie interests, and food preferences.

PLEASE NOTE: The Life Story Questionnaire will be completed 1-30 days after the informed consent document is signed.

Intervention Period Data Collection

n/a (Family Members will not be involved in the Intervention Period)

Post-Treatment Assessments

n/a (Family Members will not be involved Post-Treatment)

TIMELINE AND VISIT SCHEDULE

PWD Timeline and Visit Schedule					
Assessment / Interview / Data to Collect	Screening (Days 1-7)	Baseline Interview, Chart Review, and Observations (Days 8-30)	Treatment Visits (Days 31-60, three visits per week)	Post-Treatment Interview (Days 61-74)	
Informed Consent Form (Legally Authorized Representative)	X				
Assent (Person with Dementia)	X				
Confirm Age 65+ (Chart Review)	X				
Confirm Read & Speak English (Chart Review)	X				
Confirm Dementia Diagnosis (Chart Review)	X				
Confirm Exclusion Criteria Do Not Apply to the PWD (Chart Review)	X				
Neuropsychiatric Interview – Nursing Home (NPI-NH) (Proxy Interview)	X				
Enrollment (if eligible)	X				
Brief Interview for Mental Status (BIMS) (Direct Interview)		X			
Dementia Quality of Life (DEMQOL) (Direct Interview or Proxy if unable to respond)		X			
Document All Diagnoses, Type of Dementia, Meds, and Demographics (Chart Review)		X			
Observations of PWD in Standard Activities w/ Menorah Park Engagement Scale (MPES)		X			
Observations of PWD in Standard Activities w/ Engagement for PWD Scale (EPWDS)		X			
Treatment Fidelity / Process Measures			X		
Observations of PWD during BRAIN activities using the MPES			X		
Observations of PWD during BRAIN activities using the EPWDS			X		
Satisfaction Questions			X		
DEMQOL (Direct Interview or Proxy, if PWD unable to respond)				X	
NPI-NH (Proxy Interview)				X	

Staff Members Timeline and Visit Schedule				
Assessment / Interview / Data to Collect	Screening (Days 1-7)	Baseline Interview, Chart Review, and Observations (Days 8-30)	Treatment Visits (Days 31-60, three visits per week)	Post-Treatment Interview (Days 61-74)
Informed Consent Form	X			
Confirm Age 18+ (Direct Interview)	X			
Confirm Read & Speak English (Direct Interview)	X			
Confirm Staff Does Not Only Work Third Shift (Direct Interview)	X			
Enrollment (if eligible)	X			
Quality of Carer-Patient Relationship (QCPR)		X		
Pre-Training Quizzes for Training Modules		X		
Take Two Training Modules			X	
Learning Management System Automatically Collects Basic Training Data			X	
Post-Training Quizzes for Training Modules			X	
Treatment Fidelity / Process Measures			X	
Satisfaction Questions			X	
Quality of Carer-Patient Relationship (QCPR)				X

Family Members Timeline and Visit Scheudle			
Assessment / Interview / Data to Collect	Baseline & Screening (Days 1-30)		
Informed Consent Form	X		
Confirm Age 18+ (Direct Interview)	X		
Confirm Read & Speak English (Direct Interview)	X		
Enrollment (if eligible)	X		
Life Story Questionnaire	X		

VISIT PROCEDURES

PWD

Screening Procedures

Chart Review for Eligibility Criteria

After consent is obtained from the PWD's legally authorized representative and the PWD him/herself provides assent, a researcher will schedule a time with staff at the nursing or assisted living to review eligibility information in his/her chart (i.e., age 65+, able to read and speak English, diagnosed with dementia (of any type), NOT bed confined, NOT completely unable to communicate verbally, does NOT have serious visual or hearing impairments, and does NOT show signs of rapid cognitive decline or physical deterioration over the last 6 months).

NPI-NH Interview

A researcher will then schedule a time to interview a staff member familiar with the PWD to conduct the NPI-NH. The researcher will follow standard protocol for conducting the NPI-NH and be extensively trained on how to properly use the measures.

Baseline Procedures

Baseline Assessment

A researcher will schedule a time to work with the PWD and conduct a direct interview with him/her to complete the DEMQOL and BIMS. The researcher will follow standard protocol for conducting these measures and be extensively trained on how to properly use these measures. *Please note that the BIMS is not an outcome measure. The BIMS is exclusively being conducted so that we can describe the level of impairment of the study sample.*

Chart Review

A researcher will schedule a time with staff at the nursing or assisted living to collect the following data from his/her chart:

- All diagnoses
- Type of dementia
- All meds
- Demographics (race/ethnicity, education level, marital status, and number of years living in LTC)

Observations of Standard Activities

Researchers will observe the PWD taking part in standard activities using the MPES and EPWDS. At least 12 observations will be taken with each measure, so that an average score can be calculated for baseline, standard activity programming. Researchers will follow the standard protocols for using the MPES and EPWDS and be extensively trained on how to properly use these measures.

Intervention Period Procedures

The PWD will be invited to participate in three BRAIN sessions per week for four weeks. The sessions will be facilitated by a staff member at the nursing home or assisted living facility. The staff member will be trained on how to conduct BRAIN Sessions.

Treatment Fidelity / Process Measures

Researchers will complete a Session Summary Form for each scheduled session, even if the session does not actually occur due to the PWD's unavailability or refusal to participate. The following data will be collected on the Session Summary form: PWD ID#, Date of Session, Time of Session, Facilitator ID#, Did the PWD attend the session? (Yes/No), If NO to previous question, please indicate why the PWD did not attend? (Unavailable / Refused / Other), Reason for unavailability or refusal, and Length of Session. Data will be based upon the researchers observation of the actual session taking place. Researchers will be extensively trained on how to properly use the Session Summary Form.

Observations of BRAIN Sessions

Researchers will observe the PWD taking part in BRAIN sessions using the MPES and EPWDS. At least 12 observations will be taken with each measure, so that an average score can be calculated for BRAIN activity programming. Researchers will follow the standard protocols for using the MPES and EPWDS and be extensively trained on how to properly use these measures.

Satisfaction Questions

Researchers will pose the following questions to the PWD at the end of each BRAIN Session. At the end of each session a researcher will pose the following three questions to the PWD: Did you enjoy the activity? Yes/No, Would you do an activity like this again sometime? Yes/No, Would you recommend this activity to others? Yes/No

Post-Treatment Procedures

Post-Treatment Assessment

A researcher will schedule a time to work with the PWD and conduct a direct interview with him/her to complete the DEMQOL.

NPI-NH Interview

A researcher will schedule a time to interview a staff member familiar with the PWD to conduct the NPI-NH.

Staff Members

Screening Procedures

Direct Interview for Eligibility Criteria

After consent is obtained from the staff member, a researcher will interview the staff member to confirm that he/she meets the following eligibility criteria:

- a. The Staff Member is age 18+
- b. The Staff Member is able to read and speak English
- c. The Staff Member does not only work third shift

Baseline Procedures

Baseline Interview

A researcher will conduct a direct interview with the staff member to conduct the QCPR. The researcher will follow standard protocols for using the QCPR and be extensively trained on how to properly use the measure.

Pre-Training Quizzes for Training Modules

Staff will be asked to complete two 15-item quizzes--i..., one 15-item quiz for "Training Module 1: Using the BRAIN App" and one 15-item quiz for "Training Module 2: Top 10 Tips for Facilitating Activities with Persons with Dementia." All questions will be multiple choice in nature. Staff will complete the quizzes independently on a computer, tablet, or smartphone

Intervention Period Procedures

Take Two Training Modules

A researcher will show the staff member how to access the online training and then take the two online training modules: Training Module 1: Using the BRAIN App and Training Module 2: Top 10 Tips for Facilitating Activities with Persons with Dementia

Learning Management System Automatically Collects Basic Training Data

The Learning Management System will automatically collect two pieces of data for each training module. Did the Staff Member complete the training module? (Yes/No). How long did it take for the Staff Member to complete the training module (in minutes)? A researcher will enter these data into the participant's digital binder.

Post-Training Quizzes for Training Modules

After completing each training module, the Staff Member will be presented with the two 15-item quizzes that were presented to them at baseline (although the order of the questions will be changed).

Treatment Fidelity / Process Measures

The Staff Member will facilitate three BRAIN sessions per week for four weeks (per PWD).

A Session Summary Form will be completed for each scheduled session, even if the session does not actually occur due to the PWD's unavailability or refusal to participate. The following data will be collected on the Session Summary form: PWD ID#, Date of Session, Time of Session, Facilitator ID#, Did the PWD attend the session? (Yes/No), If NO to previous question, please indicate why the PWD did not attend? (Unavailable / Refused / Other), Reason for unavailability or refusal, and Length of Session.

Satisfaction Questions

At the end of each session a researcher will pose the following four questions to the staff member: Did you enjoy facilitating the activity? Yes/No, Do you think the PWD enjoyed the activity? Yes/No, Would you facilitate an activity like this again sometime? Yes/No, and Would you recommend this activity to your colleagues? Yes/No

Treatment Fidelity / Process Measures

Researchers will complete a Session Summary Form for each scheduled session, even if the session does not actually occur due to the PWD's unavailability or refusal to participate. The following data will be collected on the Session Summary form: PWD ID#, Date of Session, Time of Session, Facilitator ID#, Did the PWD attend the session? (Yes/No), If NO to previous question, please indicate why the PWD did not attend? (Unavailable / Refused / Other), Reason for unavailability or refusal, and Length of Session. Data will be based upon the researchers' observation of the actual session taking place. Researchers will be extensively trained on how to properly use the Session Summary Form.

Observations of BRAIN Sessions

Researchers will observe the PWD taking part in BRAIN sessions using the MPES and EPWDS. At least 12 observations will be taken with each measure, so that an average score can be calculated for BRAIN activity programming. Researchers will follow the standard protocols for using the MPES and EPWDS and be extensively trained on how to properly use these measures.

Satisfaction Questions

Researchers will pose the following questions to the PWD at the end of each BRAIN Session. At the end of each session a researcher will pose the following three questions to the PWD: Did you enjoy the activity? Yes/No, Would you do an activity like this again sometime? Yes/No, Would you recommend this activity to others? Yes/No

Post-Treatment Procedures

Post-Treatment Interview

A researcher will schedule a time to work with the staff member and conduct a direct interview with him/her to complete the QCPR.

Family Members

Screening Procedures

Direct Interview for Eligibility Criteria

After consent is obtained from the family member, a researcher will interview the staff member to confirm that he/she meets the following eligibility criteria:

- a. The Staff Member is age 18+
- b. The Staff Member is able to read and speak English

Baseline Procedures

Baseline Interview

A researcher will invite the family member to fill out the Life Story Questionnaire, which he/she will fill out on a computer, smartphone, or tablet. This questionnaire will provide background information about their loved one / the PWD. This is the family member's only involvement in the study.

Intervention Period Procedures

N/A (Family Members do not participate in the Intervention Period)

Post-Treatment Procedures

N/A (Family Members do not participate in Post-Treatment)

FOLLOW-UP

The intervention period in this low-risk study of a non-pharmacological intervention is just one month in length. As such, follow up is not required. The final point of contact for PWD and staff member will be the post-treatment assessment / interview.

EARLY DISCONTINUATION

Participants are free to withdraw from participation in the study at any time and for any reason.

REMOVED ON 8/31/21 If they do withdraw, we will continue to follow them, with their permission.

SAFETY REPORTING

For the purposes of this study, a participant is considered enrolled if they have successfully completed the screening procedure outlined above. This study will be monitored by an NIA approved Safety Officer (SO). The SO Will follow the procedures and protocols laid out in this document as well as the DSMP.

After being enrolled in the study, participant safety will be monitored regularly by the PI with reports being sent to the SO twice per year.

As this is a minimal risk psychosocial activity intervention no AEs or SAEs are expected per NIH definitions, as none of the risks of the study will affect medical outcomes or occurrences. However, if any AEs do occur, whether they appear study-related or not, they will be reported to the SO and the IRB within 48 hours of occurrence. Any deaths to study participants, from whatever cause, will be reported within 24 hours. The SO and IRB will then make the determination of whether they should be reported to the NIA.

If any AEs or SAEs occur, the PI will, with the assistance of the SO and IRB, determine if any modifications need to be made to the study protocol and procedures. As this is a minimal risk study, this is highly unlikely.

Specification of Safety Parameters

As this is a non-medical, short duration trial with no interim measures (pre-post design), there are no lab values or test scores that fill this role. If a participant becomes agitated during an activity they will be redirected and the programming will stop. If this occurs at a clinical level that then results in an AE it will be reported to the SO.

Methods and Timing for Assessing, Recording, and Analyzing Safety Parameters

The risk profile for this study is low as it is a minimal risk, nonpharmacologic intervention. As such, assessing and recording of the parameters will be done by the PI with the end goal of informing the

